23.2.5 Treatment Failure

A treatment failure is defined as stopping a preventive medication with the reason being lack of efficacy, safety/tolerability or contraindications.

23.2.6 Treatment Resistant

The definition of a participant being treatment resistant is inspired by a published guideline⁶ and the following criteria should be fulfilled for a participant to be treatment resistant:

1. At least 12 severe CH attacks during the Screening Period
2. At least three treatment failures with three different preventive medications prior to the Screening Visit

23.2.7 Sustained Response

A participant will be eligible to count as a sustained responder if:

- The first month is a response
- At least 50 % of the following months are observed
- Month 12 should be observed
- All observed months from the first month until Month 12 is a response

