
• To evaluate the efficacy of eptinezumab on health-related quality of life, health care resource utilization, and work productivity	
- Patient Global Impression of Change (PGIC) score at Weeks 4, 8, ..., 48- Change from Baseline in the Sleep Impact Scale (SIS) domain scores at Weeks 4, 12, 16, 24, 28, 36, 40, 48 - Exploratory endpoints:- Change from Baseline in the number of monthly attacks (Months 1, 2, ..., 12)- Change from Baseline in the pain per attack, as assessed using the 5-point self-rating pain severity scale (Months 1, 2, ..., 12)- Response: $\geq 30\%$ reduction from Baseline in the number of monthly attacks (Months 1, 2, ..., 12)- Response: $\geq 50\%$ reduction from Baseline in the number of monthly attacks (Months 1, 2, ..., 12)- Response: $\geq 75\%$ reduction from Baseline in the number of monthly attacks (Months 1, 2, ..., 12)- Response: 100% reduction from Baseline in the number of monthly attacks (Months 1, 2, ..., 12)- Change from Baseline in the monthly number of times an abortive therapy (oxygen and/or triptans, only oxygen, and only triptans) was used (Months 1, 2, ..., 12)- Change from Baseline in the weekly integrated measure of frequency and intensity of attack related pain, that is, the sum of the intensity (worst pain on a 5-point self-rating pain severity scale) for each attack during a week (Weeks 1, 2, 3, 4, 13, 14, 15, 16, 25, 26, 27, 28, 37, 38, 39, 40) or the intensity of attack related pain multiplied by the weekly number of attacks (Weeks 5, 6, ..., 12, 17, 18, ..., 24, 29, 30, ..., 36, 41, 42, ..., 48)- Use of triptans (Weeks 1-48)- Use of oxygen (Weeks 1-48)- Use of preventive medication (Weeks 1-48)- Sustained response: $\geq 75\%$ reduction from Baseline in the number of monthly attacks for any month, where all the subsequent months also had $\geq 75\%$ reduction from Baseline in the number of monthly attacks (Months 1, 2, ..., 12)- A maximum score of mild on the 5-point self-rating pain severity scale (Weeks 1, 2, ..., 48) - Secondary endpoints:- Change from Baseline in the EuroQol 5-Dimension 5-Level (EQ-5D-5L) score at Weeks 4, 16, 28, 40, and 48- Health Care Resources Utilization (HCRU) at Baseline and Weeks 4, 16, 28, 40, and 48- Change from Baseline in the Work Productivity Activity Impairment: General Health second version (WPAI:GH2.0) subscores (Absenteeism, Presenteeism, Work productivity loss, Activity impairment) at Weeks 4, 16, 28, 40, and 48

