13.5.6.2 Efficacy Endpoints Regarding Response

For endpoints regarding response (30%, 50%, 75% or 100%) or sustained response (75%), the number and percentage of responders using weekly number of attacks for Week 1, Week 2, Week 3, Week 4, Week 5,, Week 48 and the number and percentage of responders using monthly number of attacks for Month 1, Month 2,, Month 12 will be presented without imputations other than described in section [13.5.1.1.1](#). Additionally, sensitivity analyses will be made using LOCF and worst case imputations, for further details see section [13.5.9.3](#). For all of these analyses DPS3 will be used when determining whether a participant is a responder or not.

Furthermore, the number and percentage of responders will be found for the following periods of time (for details see section [23.2.1.7](#)):

- Months 1-3, Months 4-6, Months 7-9, Months 10-12
- Months 1-6, Months 7-12

- Months 1-12

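### Sustained 75% response has no minimum duration: if the series may start in any month, a response in Month 12 alone counts as sustained, and a table by start month rises by construction

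*SAP*

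**What the plan says.** Panel 2 (SAP section 5) lists sustained response among the exploratory endpoints: a reduction of at least 75% in monthly attacks "for any month, where all the subsequent months also had" that reduction, indexed over Months 1 to 12. SAP section 22 repeats the any-month wording and says the endpoint was added for completeness.

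SAP section 23.2.7 gives four conditions:

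- On how the series begins, it asks that "The first month is a response".
- On missing data, half or more of the later months must have an observation.
- The final month of the trial, Month 12, must itself have an observation.
- On the run as a whole, it asks that "All observed months from the first month until Month 12 is a response".

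On presentation, SAP section 13.5.6.2 reads "For endpoints regarding response (30%, 50%, 75% or 100%) or sustained response (75%), the number and percentage of responders" and runs the monthly display from Month 1 to Month 12. It adds: "For all of these analyses DPS3 will be used when determining whether a participant is a responder or not". Response of at least 75% in each single month, Month 12 included, is a separate exploratory endpoint in Panel 2. Section 23.2.1.7 defines a percentage denominator for 3-, 6- and 12-month response periods. None is given for sustained response.

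**The concern.** A sustained response should need more than one month of response. Neither Panel 2 nor section 23.2.7 says how many months are needed or when the series must have begun at the latest. The SAP's other duration endpoints do set a minimum: at least 4 weeks for remission (23.2.1.9) and at least 12 or 13 weeks for conversion (23.2.1.8 gives both).

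Two things are at stake. First, the term first month in 23.2.7 has two readings. One makes part of the endpoint a copy of Month 12 response, and the other conflicts with Panel 2, so a programmer cannot settle it from the text. Second, a table by start month will tend to rise towards Month 12 because later starts have fewer months to satisfy. In an open-label single-arm trial that rise could be taken for a growing effect.

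**Working it through.** The plan states no figure for this endpoint, so the check is of the rule itself.

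**Inputs from the SAP:** the four conditions in 23.2.7 and start months m = 1 to 12 from Panel 2. **Inputs not in the documents, assumed:** a constant monthly 75% response probability p of 0.3 to 0.5, and a within-participant correlation ρ of 0 to 0.8.

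**1. Which participants qualify, if the first month is the start month.**

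- Start at m = 12: the start month is a response, Month 12 is observed, and all months from 12 to 12 are responses. The following months number zero, so the 50% condition is 0 of 0 and excludes nobody.
- Start at m < 12: the last two conditions still force Month 12 to be an observed response.

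So a participant is sustained from some start month if and only if Month 12 is an observed response. Enumeration confirms this. Each month can be response, non-response or missing, giving 3^12 = 531,441 patterns. Those with a Month 12 response number 3^11 = 177,147. Those meeting the rule for some start month also number 177,147, with 0 mismatches. Eleven non-response months followed by one response qualifies.

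The SAP does not say how to treat 0 of 0. If it were treated as a failure, a Month 12 start would drop out and the shortest qualifying series would be Months 11 and 12.

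**2. If the first month is Month 1.** A lone Month 12 response then fails, but only one start month is possible, which contradicts the any-month wording and the Months 1 to 12 index in Panel 2.

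**3. Shape of a table by start month.** With complete data, response in all of months m to 12 implies response in all of months m+1 to 12. There are 0 violations in the 2^12 = 4,096 complete patterns, so the count cannot fall as m increases. For independent months,

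P(sustained from m) = p^(13 − m).

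At p = 0.4 this is 0.4^12 = 0.002% for m = 1, 0.4^3 = 6.4% for m = 10, 0.4^2 = 16% for m = 11 and 40% for m = 12. With correlation, the Month 11 row is p² + ρp(1 − p). At ρ = 0.6 that is 0.16 + 0.6 × 0.24 = 30.4%, against 30.6% simulated.

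Results with the monthly response rate flat at 40% and complete data (ρ = 0 from the formula; the other rows from a beta-binomial simulation of 40,000 participants each):

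| ρ | Start Month 1 | Month 7 | Month 10 | Month 11 | Month 12 |
|---|---|---|---|---|---|
| 0 | 0.002% | 0.4% | 6.4% | 16.0% | 40.0% |
| 0.3 | 3.2% | 7.4% | 15.7% | 23.2% | 40.4% |
| 0.6 | 14.9% | 19.7% | 26.0% | 30.6% | 40.4% |
| 0.8 | 26.5% | 29.5% | 33.0% | 35.2% | 40.0% |

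**4. Missing data and denominator.** At p = 0.4 and ρ = 0.6, with 20% dropout and 5% intermittent missing months, the rows rise from 11.0% to 30.7% of all participants. Month 12 response is 30.7% of all participants but 40.2% of those observed at Month 12. The sets of participants are identical, but the rates agree only on a common denominator. Missing months can also break the nesting (36,410 of the 531,441 patterns). With ρ = 0.9, 20% dropout and 20% intermittent missing, small local dips appear, yet the series still goes from 17.1% to 25.8%.

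**5. Effect of a latest start month.** With complete data, requiring a start by Month 10 gives the Month 10 column above: 6.4% to 33.0% instead of about 40%. In the simulations it gives 2.7% to 23.5% at p = 0.3 and 12.4% to 42.5% at p = 0.5.

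**The case against.** The strongest reply is that Panel 2 and section 13.5.6.2 point to a table by start month, not to a single pooled proportion. In that table the Month 1 row allows no observed non-response over 12 months, the Month 7 row none over 6 and the Month 10 row none over 3. With complete data, differences between rows already give the distribution of start months. The plain monthly 75% response is shown as well and would reveal a flat rate. The endpoint is exploratory, and no formal testing is planned (SAP section 13.2).

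Most of this stands, and it rules out several inferences a reader might draw:

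- That the endpoint shows no durability at all. The early rows do show it.
- That the SAP will headline an any-month rate that merely repeats Month 12 response. No such pooled figure is clearly planned.
- That the Month 1 reading gives a rate several times lower. At p = 0.4 and ρ = 0.8 it is 26.5% against 40.0%, a ratio of about 1.5.
- That the table must mislead. It would if read as a trend; correct labelling would prevent that, but the SAP does not label it as cumulative.
- That durability across dosing cycles is the endpoint's stated purpose. The documents do not say so.

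The reply does not remove the ambiguity of the first month, the last two rows that need only two months and one, the unstated handling of 0 of 0, or the missing denominator.

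**Conclusion.** The concern holds in this limited form. With the first month read as the start month, and 0 of 0 taken as meeting the 50% condition, sustained response from any start is the same set of participants as 75% response in Month 12. That result needs no assumption about response rates. With the first month read as Month 1, section 23.2.7 contradicts Panel 2. Either way the text needs an edit.

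In a table by start month, complete data guarantee counts that never fall, so a rise is not evidence of growing benefit. The rise is strict only if some participants change status between months. Its size, and the drop after a latest start month is set, depend on response rates and correlations that the documents do not give. The effect is on the interpretation of one exploratory endpoint. No error rate, estimand or safety conclusion is touched.

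**What to change.** In SAP section 23.2.7, Panel 2 and section 22:

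- Replace the first month with the start month of the series, and prespecify a latest start month. Month 10 gives a span of at least 3 months, one infusion interval. Another prespecified minimum would also do.
- Keep the existing conditions: at least 50% of the following months observed, Month 12 observed, and every observed month a response. Without the 50% rule, a participant seen only in Months 1 and 12 would count as sustained for 12 months. The present rule excludes that participant, who has 1 of 11 following months observed where at least 6 are needed. Note that a Month 10 start with Month 11 missing would still pass, at 1 of 2.
- State the denominator for the percentage.
- Report one proportion with the distribution of start months. Alternatively, label the table as cumulative by start month and omit start Months 11 and 12.

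The cost is a few lines of SAP text and one derivation. The downside is a lower reported sustained response rate.

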23.2.8 Maximum Score of Severity of Pain

The maximum score of severity of pain should be mild. In case of weeks with 0 attacks the severity will be considered to be mild or less. Furthermore, data need to have been observed for at least 4 days in a week to be able to assess if a participant fulfils the criterion about maximum score of severity being mild.

23.2.9 Patient Global Impression of Change (PGIC)

The PGIC is a single participant-reported item reflecting the participant's impression of change in their disease status since the Baseline Visit (that is, in relation to activity limitations, symptoms, emotions, and overall quality of life). The item is rated on a 7-point scale, where a low score indicate improvement from 1 (very much improved) to 7 (very much worse).

23.2.10 Sleep Impact Scale (SIS)

The SIS⁷ is a participant-reported scale to assess quality of life resulting from sleep disturbance. The SIS questionnaire includes 35 items belonging to 7 domains to assess sleep impact on: daily activities (5 items); emotional well-being (4 items); emotional impact (4 items); energy/fatigue (5 items); social well-being (6 items); mental fatigue (3 items); and satisfaction with sleep (8 items). Each item, for 6 out of the 7 domains, is rated on a 5-point scale ranging from 1 ("always" or "all of the time") to 5 ("never" or "none of the time"),

whereas satisfaction with sleep is rated on a 5-point scale ranging from 1 (very satisfied) to 5 (very dissatisfied). Items within each domain were summed and transformed using the formula $[(\text{sum of the items} - \text{number of the items}) / \text{range of the domain}] * 100$ yielding a score on a 0-100 scale.

A higher score indicated better quality of life (reverse scoring for the satisfaction with sleep domain).

Due to the technical build it will not be possible to have some missing values for a visit. Either all values will be there or none.

23.2.11 Euroqol 5 Dimension – 5 Levels (EQ-5D-5L)

The EQ-5D-5L⁸ is a participant-reported assessment designed to measure the participant's well-being. It consists of 5 descriptive items (mobility, self-care, usual activities, pain/discomfort, and depression/anxiety) and a visual analogue scale (VAS) of the overall health state. Each descriptive item is rated on a 5-point index ranging from 1 (no problems) to 5 (extreme problems) and a single summary index (from 0 to 1) can be calculated. The VAS ranges from 0 (*worst imaginable health state*) to 100 (*best imaginable health state*). The respondents rate their overall health on the day of the interview on a 0–100 hash-marked, vertical visual analogue scale.

Due to the technical build it will not be possible to have some missing values for a visit. Either all values will be there or none.

23.2.12 Health Care Resource Utilization (HCRU)

Cluster headache-specific healthcare resource utilization information will be collected in terms of outparticipant health care professional visits, emergency room visits, hospital admissions as well as number of overnight hospital stays during the past 4 weeks. Clinical site personnel and participants will be instructed to capture utilization that takes place outside of visits associated with their participation in the clinical trial.

23.2.13 Work Productivity and Activity Impairment: General Health version 2 (WPAI:GH2.0)

The WPAI:GH2.0⁹ is a participant self-rated scale designed to provide a quantitative measure of the work productivity and activity impairment due to a health condition. The WPAI:GH2.0 assess activities over the preceding 7 days and consists of 6 items: 1 item assess employment (yes/no); 3 items assess the number of hours worked, the number of hours missed from work due to the participant's condition, or due to other reasons; and 2 visual numerical scales to assess how much the participant's condition affects their productivity at work and their ability to complete normal daily activities.

The derivation of the WPAI:GH2.0 sub-scores¹⁰ is given in [Panel 7](#), where Q1-Q6 refers to question 1-6 in the questionnaire.

Panel 7 Derivation of WPAI:GH2.0 sub-scores

Sub-score	Description	Derivation
Absenteeism	Percent work time missed due to health problems	$100 * Q2 / (Q2 + Q4)$
Presenteeism	Percent impairment while working due to health problems	$100 * Q5 / 10$
Work productivity loss	Percent overall work impairment due to health problems	$100 * \left(\frac{Q2}{Q2 + Q4} + \left(1 - \frac{Q2}{Q2 + Q4} \right) * \frac{Q5}{10} \right)$
Activity impairment	Percent activity impairment due to health problems	$100 * Q6 / 10$

If the answer to Q1 (Are you currently employed (working for pay)?) is ‘Yes’ but Q2 (During the past seven days, how many hours did you miss from work because of your health problems?) and Q4 (During the past seven days, how many hours did you actually work?) are both 0, then the derived scores for Absenteeism and Work productivity loss score will be set to missing.

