Each SIS domain score, the EQ-5D-5L VAS and each WPAI:GH2.0 sub-score will be analysed using the MMRM from section [13.5.1.2](#) considering FAS with the relevant time variable and appropriate baseline value (not log-transformed) as well as the same approach for choice of covariance structure to be applied.

PGIC will be analysed using the MMRM from section [13.5.1.2](#) considering FAS with the relevant time variable and no baseline value as well as the same approach for choice of covariance structure to be applied.

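### The WPAI scoring rule for weeks with no hours worked is incomplete: Presenteeism stays scorable, and a 100% work loss becomes missing if Q5 is blank

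*SAP*

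**What the plan says.** SAP 23.2.13, Panel 7, derives three work-related sub-scores from three items: Q2 ("During the past seven days, how many hours did you miss from work because of your health problems"), Q4 ("During the past seven days, how many hours did you actually work") and Q5 (effect of health on productivity at work, divided by 10 in the formulas).

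- Absenteeism = 100 × Q2/(Q2 + Q4).
- Presenteeism, described as "Percent impairment while working due to health problems", = 100 × Q5/10. There is no condition on Q4.
- Work productivity loss, described as "Percent overall work impairment due to health problems", = 100 × [Q2/(Q2 + Q4) + (1 − Q2/(Q2 + Q4)) × Q5/10].

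The single exception is for Q1 = Yes (employed): if Q2 and Q4 "are both 0, then the derived scores for Absenteeism and Work productivity loss score will be set to missing". Nothing is said about Q2 > 0 with Q4 = 0, about a blank Q5, or about whether Q5 is asked when no hours were worked. Protocol 9.3.1.4 adds no scoring or skip rule.

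For EQ-5D-5L (SAP 23.2.11) the plan states: "Due to the technical build it will not be possible to have some missing values for a visit". The SIS section (23.2.10) makes the same statement; the WPAI section does not.

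Change from baseline in the WPAI sub-scores is a secondary endpoint (SAP chapter 5, Panel 2). SAP 13.5.6.1 says: "Each SIS domain score, the EQ-5D-5L VAS and each WPAI:GH2.0 sub-score will be analysed using the MMRM", with the baseline value in the model.

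**The concern.** Zero hours worked can arise in two ways: nothing was missed for health (Q2 = 0), or the whole week was missed for health (Q2 > 0). The exception deals with the first, and only in part. The second is the worst result that the work-loss scale can record, and it has no rule.

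Two things are at stake. First, Presenteeism is meant to rate work that was done. A Q5 answer given for a week without work has nothing to rate, yet it enters the analysis as a value between 0 and 100. Second, Work productivity loss contains Q5. When Q4 = 0 and Q2 > 0, Q5 has weight zero, but a blank Q5 still makes the computed result missing.

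In the second situation missingness is triggered by the outcome being at its maximum. A missing score at Visit 2 leaves no baseline, because WPAI is first collected there (protocol Panel 2; SAP 23.3.1). The participant then has no change score for that sub-score at any visit. The sensitivity analyses in SAP 13.5.9 concern attack counts and 75% response, so none would show the problem.

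**Working it through.** The plan gives no worked WPAI figure to reproduce, so the check applies the Panel 7 formulas and the one exception to boundary records.

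Inputs: the formulas and the exception come from SAP 23.2.13. Forty hours for a full week is an illustrative assumption; any Q2 > 0 with Q4 = 0 gives Q2/(Q2 + 0) = 1. The documents do not say what happens to Q5 when Q4 = 0, so both cases are shown. A blank Q5 is carried through as missing, the default in SAS arithmetic (SAS is the software named in SAP chapter 21).

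Ordinary week, (Q2, Q4, Q5) = (20, 20, 5):
- Absenteeism = 100 × 20/40 = 50
- Presenteeism = 100 × 5/10 = 50
- Work productivity loss = 100 × (0.5 + 0.5 × 0.5) = 75

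The formulas behave as intended.

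Whole week missed for health, (40, 0, Q5):
- Absenteeism = 100 × 40/40 = 100
- Work productivity loss = 100 × (1 + 0 × Q5/10), which is 100 for any recorded Q5 and missing if Q5 is blank, because 0 × missing is missing
- Presenteeism = 100 × Q5/10 if Q5 is recorded

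| Q2 | Q4 | Q5 | SAP: Absenteeism / Presenteeism / Work loss | With the fix |
|---|---|---|---|---|
| 20 | 20 | 5 | 50 / 50 / 75 | 50 / 50 / 75 |
| 40 | 0 | 0 | 100 / 0 / 100 | 100 / missing / 100 |
| 40 | 0 | 5 | 100 / 50 / 100 | 100 / missing / 100 |
| 40 | 0 | 10 | 100 / 100 / 100 | 100 / missing / 100 |
| 40 | 0 | blank | 100 / missing / missing | 100 / missing / 100 |
| 0 | 0 | 5 | missing / 50 / missing | all missing |
| 0 | 0 | blank | all missing | all missing |

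Direction of bias if Q5 is blank. A participant at 100 at baseline who later scores x has a true change of x − 100, which is zero or an improvement. Losing such participants tends to understate mean improvement. A participant with baseline b who later scores 100 has a true change of 100 − b, which is zero or a worsening. Losing those weeks tends to overstate improvement. The balance depends on how many of each occur, and the documents give no figure for either.

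**The case against.** The strongest counter-argument is that nothing shows Q5 can be blank for an employed participant. If the device requires an answer, the 100% score is always kept. The all-or-none sentence may be absent from the WPAI section only because work items do not apply to people who are not employed. Panel 7 also cites an outside scoring source that cannot be consulted here, and it may settle the case. That Presenteeism should be missing at Q4 = 0 rests on its description in Panel 7, not on a stated scoring rule.

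Much of this stands, and it limits the point. It does not remove it: if Q5 is always recorded, the loss of the 100% score disappears, but Presenteeism is then scored for weeks without work. That includes Q2 = Q4 = 0, the very case the SAP set out to handle.

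Three stronger readings are tempting, and the documents do not support them.

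- A reader might infer that the stated exception itself deletes the 100% score. It does not apply when Q2 > 0, and Panel 7 then returns 100 for any recorded Q5.
- A reader might infer that some sub-score is wrong however Q5 is collected. That is true for Q2 > 0 with Q4 = 0. It is false for Q2 = Q4 = 0 with Q5 blank, where all three scores are missing, as they should be.
- A reader might infer that the gap flatters treatment by a calculable number of points. Any such number needs an assumed share of fully missed weeks and an assumed mean for the others. It would describe a raw visit mean rather than change from baseline, would be zero if Q5 is always recorded, and would ignore the opposite pull of lost 100% baselines.

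**Conclusion.** The gap is real and minor. Applied literally to an employed participant who missed the whole week for health, SAP 23.2.13 mis-scores exactly one sub-score: Presenteeism if Q5 is recorded, Work productivity loss if it is blank. The two errors cannot occur in the same record. In the Q2 = Q4 = 0 case, Presenteeism also remains scorable whenever Q5 is recorded.

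The Presenteeism part assumes that the sub-score means what its description in Panel 7 says. The Work productivity loss part assumes a blank Q5 and literal coding; the documents neither confirm nor exclude the blank. The MMRM would not repair that loss, because missingness would depend on the unrecorded score itself.

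No size can be given for the effect on the endpoint, and its net direction is undetermined. The reach is limited to two of the four sub-scores, to employed participants, and to weeks with zero hours worked. The trial's primary objective is safety, there are no key secondary endpoints (SAP 13.4), and no formal testing is planned (SAP 13.2).

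**What to change.** Add to SAP 23.2.13:

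- If Q1 = Yes, Q2 > 0 and Q4 = 0, then Absenteeism = 100 and Work productivity loss = 100, irrespective of Q5.
- Whenever Q4 = 0, Presenteeism = missing.

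The existing rule for Q2 = Q4 = 0 stays. The addition is right whether or not Q5 is collected in such weeks, and it changes no record with Q4 > 0. It would also help to state whether the device asks Q5 when Q4 = 0, so that a reader knows which case arose.

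The cost is a sentence or two in the SAP and about one line of code. The downside is slightly fewer Presenteeism values.
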